2. SYNOPSIS

Name of Sponsor: Capricor, Inc.	
Name of Investigational Product: CAP-1002 Allogeneic Cardiosphere-Derived Cells	
Name of Active Ingredient: Cardiosphere-Derived Cells	
IND Number: [REDACTED]	
Title of Trial: A Phase 2, Randomized, Double-Blind, Placebo-Controlled Trial Evaluating the Safety and Efficacy of Intravenous Delivery of Allogeneic Cardiosphere-Derived Cells in Subjects with Duchenne Muscular Dystrophy	
Trial Name: Halt myOPathy progrESSION (HOPE-2)	
Trial Centers: Up to 15 (USA)	
National Principal Investigator: [REDACTED]	
Principal Investigators: This is a multi-center trial with multiple Principal Investigators.	
Study Period: Approximately 24 months	Phase of Development: 2
Objectives: Primary: Evaluate the safety and efficacy of intravenous (IV) CAP-1002 administered every three months in subjects with Duchenne muscular dystrophy (DMD) and impaired skeletal muscle function Secondary: Evaluate the impact of repeated IV administrations of CAP-1002 on exploratory efficacy assessments of skeletal and cardiac muscle function, and quality of life	
Methodology: This Phase 2, multi-center, randomized, double-blind, placebo-controlled trial will assess the safety and efficacy of allogeneic cardiosphere-derived cells (CDCs), or CAP-1002, administered as four IV infusions, one every three months, for the treatment of subjects with DMD. Subjects with a clinical diagnosis of DMD confirmed by genetic testing and evidence of skeletal muscle impairment will undergo a battery of tests and procedures during a 30-day screening period to determine eligibility based on protocol inclusion and exclusion criteria. Eligible subjects will be prospectively randomized in stratified permuted blocks to CAP-1002 or placebo (1:1 ratio). To allow sufficient time for delivery of Investigational Product (IP), subjects must be randomized approximately 7 days in advance of their first IV infusion of Investigational Product (IP) on Day 1. Randomization will be stratified by site and entry item score of the Performance of the Upper Limb 1.2 (PUL). Subjects will undergo baseline safety and efficacy assessments (Table 3) prior to the first infusion of IP (CAP-1002 or placebo). Administration of IP (Day 1) should occur within a maximum of 14 days following randomization; if a delay of more than 14 days between randomization and IP administration is unavoidable, a conversation between the Investigator and Medical Monitor should occur to determine the need for repeat assessments prior to infusion. Subjects who are not randomized may be re-screened at the discretion of the Investigator.	

Subjects will complete study assessments at Screening; Baseline (≤ 2 days prior to Day 1); Day 1; Weeks 4 and 6 (± 7 days, each); Month 3 (± 14 days), Month 4.5 (± 14 days), and Months 6, 9, and 12 (± 14 days, each).

All IV infusions will be conducted in an outpatient setting at the investigative site on Day 1 and Months 3, 6, and 9. Prior to each IP infusion, medications will be administered to the subject as determined by the Investigator based on the pre-treatment guidelines provided by Capricor and/or institutional protocols to minimize the risk of potential severe allergic reactions such as anaphylaxis. Subjects will be observed in the outpatient setting for at least two hours post infusion and then discharged the same day if medically cleared by the site Investigator. As part of these visits, subjects will complete a safety phone call 14 days (± 3 days) after each IP infusion, and if clinically indicated, an unscheduled in-person visit will be performed at the investigative site with targeted assessments based on presentation of signs and symptoms.

Blood samples for donor-specific antibody (DSA) testing will be collected at Baseline, Week 4, 14-30 days prior to the IP infusions scheduled for the Month 3, 6 and 9 visits, and Month 12. Blood collections for clinical laboratory and DSA testing at Week 4 and pre-dose DSA testing at Months 3, 6, and 9 will occur either at the investigative site or remotely at a designated central laboratory patient service center. Blood collection for biomarker and exploratory biomarker testing at Week 6 and Month 4.5 will be conducted for those subjects who are able to travel to the investigative site.

If trial evidence suggests an appropriate risk/benefit profile of CAP-1002, Capricor, upon the recommendation of the Data Safety Monitoring Board (DSMB), will introduce an open-label extension study to offer CAP-1002 to subjects who were randomized to placebo and completed the 12-month follow-up period of the original trial.

The **primary safety endpoints** include the incidence of the following from baseline through the 12-month timepoint:

- Acute respiratory decompensation within 2 hours following IP administration
- Hypersensitivity reaction
 - Hypersensitivity reaction is defined as a clinical syndrome including, but not limited to, fever, leukocytosis, or rash with onset ≤ 2 hours post infusion and lasting < 24 hours, in the absence of clinical signs of concomitant infection.
- All-cause mortality
- Serious adverse events
- Treatment-emergent adverse events related to IP or administration procedure
- Immune sensitization syndrome
 - Immune sensitization syndrome shall be defined as: (a) clinical signs and symptoms consistent with systemic inflammation (e.g., fever, leukocytosis, rash, or arthralgia) with onset ≥ 24 hours post infusion and the absence of clinical signs of concomitant infection, **AND** (b) elevation of anti-human leukocyte antigen (HLA) antibodies against the donor cells (i.e., DSAs), detected ≤ 30 days following onset of syndrome, of (i) ≥ 2000 mean fluorescent intensity (MFI) if baseline MFI ≤ 1000 , or (ii) ≥ 2 times baseline otherwise

The **primary efficacy endpoint** is change from baseline to the 12-month timepoint in functional capacity as assessed by the mid-level (elbow) dimension of the PUL 1.2.

The **secondary safety endpoint** is the incidence and severity of all adverse events through the 12-month timepoint.

The **secondary efficacy endpoints** include the change from baseline for the following:

- Mid-level (elbow) dimension of the PUL 1.2 at Months 3, 6, and 9 (*Month 12 is the primary endpoint*)
- Regional systolic left ventricular (LV) wall thickening as assessed by cardiac magnetic resonance imaging (MRI) at Months 6 and 12

The **exploratory efficacy endpoints** include the change from baseline to each assessment timepoint for the following assessments:

- All subjects
 - High-level (shoulder) dimension of the PUL 1.2
 - High-level (shoulder) dimension of the PUL 2.0
 - Mid-level (elbow) dimension of the PUL 2.0
 - Distal-level (wrist and hand) dimension of the PUL 1.2
 - Distal-level (wrist and hand) dimension of the PUL 2.0
 - Grip strength
 - Key and tip-to-tip pinch strength
 - Elbow flexion strength
 - Slow vital capacity (SVC), forced expiratory volume in one second (FEV₁), forced vital capacity (FVC), peak expiratory flow (PEF), maximum inspiratory pressure (MIP), maximum expiratory pressure (MEP), peak cough flow (PCF), and inspiratory flow reserve (IFR)
 - LV structure and function as assessed by cardiac MRI including ejection fraction, end-diastolic volume, end-systolic volume, stroke volume, regional wall thickness, and circumferential strain
 - Biomarkers may include those for muscle inflammation (osteopontin); systemic inflammation (interleukin 1 beta [IL-1 β], IL-2, -6 and -10; tumor necrosis factor alpha [TNF- α] and C-X-C motif chemokine 10 [CXCL10]); muscle damage (troponin I [cardiac, fast skeletal, slow skeletal], troponin T, creatine kinase MM isoenzyme [CK-MM], creatine kinase MB isoenzyme [CK-MB], creatine kinase [total], creatine phosphate, and creatinine); and muscle regeneration (myostatin and follistatin)
 - DMD Upper Limb Patient-Reported Outcome Measures (DMD UL-PROM)
 - Pediatric Outcomes Data Collection Instrument (PODCI)

- DMD Lifetime Mobility Scale (DMD-LMS)
- Resource utilization including the incidence of hospitalizations for orthopedic injury or surgery, pulmonary infections, and antibiotic usage
- Ambulatory subjects only
 - 10-Meter Walk/Run Time (10MWRT)
 - Incidence of loss of ambulation (defined by 10MWRT > 30 seconds)
 - North Star Ambulatory Assessment (NSAA)

Oversight of the trial will be provided by the blinded trial Steering Committee, an independent, unblinded DSMB, and an independent, blinded Clinical Events Committee (CEC) that will adjudicate all potential primary safety endpoints.

Number of Subjects: Twenty (20) subjects will be randomized in the trial.

Diagnosis and Main Criteria for Inclusion: Subjects with DMD and evidence of skeletal muscle impairment will be evaluated for eligibility to participate in the trial.

Inclusion Criteria Assessed within 30 Days Prior to Randomization Unless Otherwise Noted:

1. Male subjects at least 10 years of age at time of consent
2. Willing and able to provide informed consent to participate in the trial if \geq 18 years of age, and assent with parental or guardian informed consent if $<$ 18 years of age
3. Diagnosis of DMD based on clinical and phenotypic manifestations consistent with DMD (e.g., family history of DMD, elevated creatine kinase, dystrophin muscle biopsy, calf pseudohypertrophy, Gowers' sign, and gait impairment before 7 years of age) with confirmatory genetic testing performed at a Clinical Laboratory Improvement Amendments (CLIA)-certified laboratory. *See exclusion criteria 4 and 5 for mutation-specific exclusions.*
4. Performance of the Upper Limb entry item score 2-5
5. If ambulatory, 10-meter walk/run velocity $<$ 1 meter/second
6. Loss of independent ambulation by 18th birthday (standing unassisted or ability to take, at most, several steps independently is not considered ambulation)
7. Receiving standard of care therapy at an experienced, multidisciplinary, DMD center as evidenced by regular cardiac and pulmonary monitoring, systemic glucocorticoid treatment, and at-home range of motion exercises
8. Treatment with a systemic glucocorticoid is required for at least 12 months prior to randomization. The dose must remain stable for at least 6 months prior to randomization with the exception of either weight-based dose adjustment or a decrease in steroid dose of \leq 10% for toxicity. For patients on chronic deflazacort, treatment with an equivalent dose of prednisone or prednisolone for a period of \leq 30 days to bridge lack of availability of deflazacort during the 6 months prior to randomization is acceptable
9. Current and up-to-date immunizations according to children and adolescent Centers for Disease Control immunization schedule, unless contraindicated, including the following: meningococcal

and meningococcal B; tetanus, diphtheria & acellular pertussis (Tdap); and pneumococcal polysaccharide vaccinations

10. Adequate venous access for parenteral IP infusions and routine blood collections in the judgement of the Investigator
11. Assessed by the Investigator as willing and able to comply with the requirements of the trial

Exclusion Criteria Assessed within 30 Days Prior to Randomization Unless Otherwise Indicated:

1. Left ventricular ejection fraction (LVEF) < 35%
2. Elbow-flexion contractures > 30° in both extremities
3. Body mass index (BMI) > 45
4. Documentation of exon 44 skip-amenable mutation(s) in the dystrophin gene (*see Appendix I for comprehensive list of mutations*)
5. Documentation of dystrophin deletion mutation(s) encompassing and limited to exons 3-7
6. Percent predicted FVC (FVC%_{op}) < 35%
7. Inability to perform consistent FVC measurements within ±15% during paired testing at screening
8. Risk of near-term respiratory decompensation in the judgment of the investigator, *or* the need for initiation of non-invasive ventilator support as defined by serum bicarbonate ≥ 29 mmol/L at screening
9. History of non DMD-related chronic respiratory disease requiring ongoing or intermittent treatment including, but not limited to, asthma, bronchitis, and tuberculosis
10. Acute respiratory illness within 30 days prior to screening
11. Initiation of non-invasive ventilation within 30 days prior to screening, or the anticipated need to initiate non-invasive ventilation within the 12 months following screening
12. Planned or anticipated thoracic or spinal surgery within the 12 months following randomization
13. Planned or anticipated lower extremity surgery within the 12 months following randomization, if ambulatory
14. Known hypersensitivity to dimethyl sulfoxide (DMSO) or bovine products
15. Initiation of treatment with metformin or insulin within 3 months prior to randomization
16. Initiation of treatment with an FDA-approved exon skipping therapy for the treatment of DMD within 24 months prior to randomization or dose adjustments to the therapy within 12 months prior to randomization with the exception of weight-based dose adjustments
17. Treatment with human growth hormone (HGH) within 3 months prior to randomization, unless on a stable dose (as determined by the site PI) for at least 24 months prior to randomization
18. Treatment with idebenone within 3 months prior to randomization
19. Treatment with a cell therapy product within 12 months prior to randomization

20. Treatment with an investigational product within 6 months prior to randomization
21. History, or current use, of drugs or alcohol that could impair their ability to comply with participation in the trial
22. Inability to comply with the investigational plan and follow-up visit schedule for any reason, in the judgment of the investigator

Investigational Product, Dosage and Mode of Administration:

[REDACTED]

[REDACTED]

Subjects assigned to CAP-1002 will receive a total dose of 150 million CDCs per administration.

Duration of Treatment: CAP-1002 (150 million CDCs) or placebo is administered once every 3 months for a total of 4 administrations.

Duration of Trial: All subjects will be followed until 12 months post Day 1.

Criteria for evaluation:

Efficacy

The following efficacy outcome measures will be performed at Months 3, 6, 9 and 12 unless otherwise specified:

- Skeletal muscle function: PUL (1.2 and 2.0), grip strength, key and tip-to-tip pinch strength, elbow flexion strength, and, if ambulatory, NSAA
- Pulmonary function: SVC, FVC, FEV₁, PEF, MIP, MEP, PCF, and IFR

- Cardiac function and structure at Month 6 and 12 only: cardiac MRI (LV ejection fraction, end-diastolic volume, end-systolic volume, stroke volume, regional systolic wall thickening, regional wall thickness, and circumferential strain)
- Quality of Life (QOL): DMD Upper Limb Patient-Reported Outcome Measures, Pediatric Outcomes Data Collection Instrument, and DMD Lifetime Mobility Scale
- Biomarker analysis at Week 6, Month 3, Month 4.5¹, and Months 6, 9, and 12 may include:
 - *Muscle inflammation:* osteopontin
 - *Systemic inflammation:* IL-1 β , IL-2, IL-6, IL-10, TNF- α , and CXCL10
 - *Muscle damage:* troponin I (cardiac, fast skeletal, slow skeletal), troponin T, CK-MM, CK-MB, creatine kinase (total), creatine phosphate, and creatinine
 - *Muscle regeneration:* myostatin and follistatin
 - Additional serum collection reserved for future biomarker analyses (i.e., exploratory biomarkers)

Safety

Safety assessments at Week 4 and Months 3, 6, 9 and 12, unless otherwise indicated, will include the following: vital signs, height, weight, physical examination, 12-lead ECG, adverse events, DSA assessment, and clinical laboratory testing (serum chemistry, hematology, and urinalysis). Adverse events and concomitant medications will also be collected during each 14-day post-infusion safety phone call, or if clinically indicated, an unscheduled in-person visit will be performed at the investigative site with targeted assessments based on presentation of signs and symptoms of subject.

Other

The medical resource utilization pharmacoeconomic analysis will explore all-cause hospitalizations, hospitalizations for orthopedic injury/surgery or pulmonary infections, and antibiotic usage. Billing information will not be collected; rather, standardized, composite or bundled costings of national averages will be used in the analysis.

Statistical Methods:

The statistical test for the primary efficacy endpoint will be two-sided and will be conducted using 0.05 significance levels. The detailed description of the trial statistical methods is provided in the Statistical Analysis Plan (SAP).

Sample Size

The trial will randomize 20 subjects.

¹ Biomarker and exploratory biomarker testing at Week 6 and Month 4.5 will be conducted only for those subjects who are able to travel to the investigative site.

Analysis Populations

The following analysis populations will be defined for the trial:

Safety Population: Subjects who begin an infusion of IP. Safety endpoints for subjects will be summarized and analyzed according to the treatment actually received.

Intent-to-Treat (ITT) Population: Subjects who were randomized. Subjects will be summarized and analyzed in the treatment group to which they were randomized.

Modified Intent-to-Treat (mITT) Population: For each efficacy parameter, the mITT population will include subjects in the ITT population who have a baseline observation (i.e., mITT populations are parameter-specific). Subjects will be summarized and analyzed in the treatment group to which they were randomized.

Per Protocol Population: Subjects who received IP with no deviations/violations that could significantly impact the completeness, accuracy and/or reliability of the trial data. The list of subjects in the per protocol population will be compiled prior to database lock.

Interim Analysis for Futility

An interim analysis was performed based on data collected for the twenty treated subjects and submitted to the DSMB for review. The DSMB made a recommendation to continue the trial as originally designed. After review of the DSMB recommendation, the Sponsor decided to continue trial follow-up for the currently enrolled subjects but to terminate further enrollment in the trial. No additional interim analyses are planned.

Safety Analysis

Safety parameters will be evaluated using the safety population. The incidence of adverse events and any serious adverse events will be summarized by event types and the proportion of subjects with those events. There are no formal tests of hypotheses associated with the primary safety endpoint.

Efficacy Analysis

The primary efficacy endpoint will be evaluated in the ITT population, with possible supportive analyses in the mITT and PP populations. Comparisons between treatment groups on efficacy endpoints will be done using repeated measures linear models. Other analyses may also be done using appropriate parametric or non-parametric methods, depending on distributions of the data and whether or not model assumptions are met. An algorithm detailing the decision-making process for performing the primary efficacy analysis, in light of features of the data that cannot be known until the data are observed (e.g., outliers), will be detailed in the SAP.

Pharmacoeconomic Analysis

The pharmacoeconomic analysis will be done using the safety population.

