13.2.4. Reporting Adverse Events

All adverse events are collected from the time of signing informed consent for trial participation until completion of 12 months or early termination, whichever occurs first. All AEs occurring after the initiation of the IV catheter placement for the initial dose of IP will be considered treatment emergent. Any ongoing adverse event that has not been resolved at the time of trial completion or early termination for a subject will be marked as ongoing on the adverse event case report form (CRF).

All AEs will be entered into the electronic data capture (EDC) system by trained site personnel at the investigative site.

Expected and unexpected SAEs must be reported to Capricor and entered into the EDC system within 24 hours of discovery of the event. For events that do not have complete information available at the time of initial report, the investigative site will submit all available information at the time of the submission. All SAE Report Forms must be signed by an Investigator and submitted with available source documentation. All source documentation must be de-identified prior to submission.

Should access to the EDC system be unavailable, SAEs and subsequent follow-up information must be reported to Capricor, or designee, via:

- Email: [REDACTED]
- Fax: [REDACTED]

All SAEs must be reported to the respective IRB in accordance with the investigative site’s policies. Copies of the submission will be collected by Capricor.

All SAEs will be reported to the DSMB at least semi-annually, or more frequently at the discretion of the Medical Monitor.

Capricor will promptly upon discovery, report serious and unexpected adverse events for which there is a reasonable possibility that the investigative therapy (i.e. administration product and/or investigative product) caused the events, to the Food and Drug Administration (FDA) in accordance with 21 CFR 312.32 regulations and ICH E2A guidelines.

For trials conducted under an investigational new drug (IND) application, FDA regulations require reporting of any serious suspected adverse reaction that is unexpected according to the current Investigator’s Brochure. A serious adverse reaction is defined as any adverse event for which there is a reasonable possibility that the drug/biologic caused the AE. For the purposes of IND safety reporting, “reasonable possibility” means there is evidence to suggest a causal relationship

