7.1 Adverse Events

AEs will be coded using MedDRA coding system (Version 21.0). Potential primary safety endpoints, described in Section 2.2.1, will be adjudicated by an independent Clinical Events Committee (CEC).

The following AEs are defined as treatment-emergent AEs (TEAEs):

- AEs occurring after the initiation of the IV catheter placement for the initial dose of IP; or
- AEs with completely missing start date, or similarly, AEs that started the same month and year as IP administration but with missing start day.

Subject listings of all adverse events as reported will be provided. A separate listing will be done for TEAEs as adjudicated by the CEC. Serious AEs, primary safety endpoints as adjudicated, TEAEs adjudicated as related to IP or administration procedure, and hypersensitivity reactions as adjudicated will be listed separately.

All summary tables will be reported using TEAEs as adjudicated by the CEC. A summary of the primary safety endpoints will be presented. In addition, TEAEs related to IP or administration procedure and hypersensitivity reactions will be summarized.

AEs will be displayed by MedDRA SOC and PT, with subjects who have the same AE counted only once for that event and subjects who have more than one AE within a SOC counted only once in that SOC. The numbers and percentages of subjects reporting an event, as well as the number of events that were reported, will be calculated by treatment group.

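### The hypersensitivity line under-counts infusion reactions, because those lasting 24 hours or more, or starting between 2 and 24 hours, are classed as neither hypersensitivity nor immune sensitization syndrome

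*Protocol*

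**What the plan says.** The primary safety endpoints appear in the Protocol Synopsis and are repeated in Protocol 7.2.1 and SAP 2.2.1 with the same time limits. Two of them describe immune-type reactions.

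- Hypersensitivity reaction: a clinical syndrome with "onset ≤ 2 hours post infusion and lasting < 24 hours", without signs of infection.
- Immune sensitization syndrome: signs of systemic inflammation with "onset ≥ 24 hours post infusion and the absence of clinical signs of concomitant infection", and in addition "elevation of anti-human leukocyte antigen (HLA) antibodies against the donor cells (i.e., DSAs), detected ≤ 30 days following onset of syndrome".

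The same list contains "Serious adverse events" and "Treatment-emergent adverse events related to IP or administration procedure". Neither has a limit on time since infusion or on duration. Protocol 13.2.4 makes the second broad: "All AEs occurring after the initiation of the IV catheter placement for the initial dose of IP will be considered treatment emergent". Under Protocol 13.2.2 an event is related if the investigator rates it probable or possible.

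Protocol 14.4.1 reports incidence separately by type of event, and Protocol 14.4 plans no hypothesis test on safety. SAP 7.1 plans a summary of the primary safety endpoints and adds that "TEAEs related to IP or administration procedure and hypersensitivity reactions will be summarized". Protocol 14.4.2 also calls for a separate listing and summary of events in the 24 hours after dosing.

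**The concern.** The two definitions leave a gap in time. They also contain a duration cap that works against the purpose of the line: an immediate reaction counts if it resolves within a day and stops counting if it persists. Someone who wants the rate of infusion reactions will go to the hypersensitivity line, because it is the one labelled for that purpose. Related TEAEs mix all kinds of event and depend on the investigator's causality rating, so that line cannot supply the rate.

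The documents show that allergic reactions are a prominent anticipated risk. Protocol 10.7 requires premedication before every infusion, and the footnotes to the schedule of assessments call for tryptase sampling when allergic signs appear. The lower edge of the gap also coincides with the minimum observation period of 2 hours (Protocol 10.8). The next scheduled safety contact is the call at 14 ± 3 days (Protocol 10.9). Reactions that begin after that minimum period are thus the ones left without an immune-reaction label.

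**Working it through.** The documents state no figure that this point could reproduce, so the check is one of logic. Take a reaction with no concomitant infection and apply the definitions.

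| Onset after infusion | Duration | Antibody rise | Hypersensitivity? | Sensitization syndrome? |
|---|---|---|---|---|
| 1 h | 6 h | either | yes | no |
| 1 h | 36 h | either | no (duration) | no (onset) |
| 12 h | 6 h or 36 h | either | no (onset) | no (onset) |
| 48 h | 6 h or 36 h | yes | no (onset) | yes |
| 48 h | 6 h or 36 h | no | no (onset) | no (antibody) |

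Now cross these with related or not and serious or not: 3 onsets × 2 durations × 2 antibody states × 2 × 2 = 48 combinations.

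- Meeting a named immune endpoint: 8 (onset 1 h, duration 6 h) + 8 (onset 48 h with antibody rise) = 16.
- Meeting neither: 48 − 16 = 32.
- Of those 32, still in the primary list because related, serious or both: 24.
- Of those 32, neither related nor serious: 8. These enter only the secondary all-AE endpoint.

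These are counts of logical cases, not probabilities. Acute respiratory decompensation within 2 hours is a separate primary endpoint and was left out of the enumeration. A long immediate reaction that included it would be counted there too.

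The last row of the table is a further gap: late onset without an antibody rise. It follows from the antibody requirement and lies outside the 24-hour window discussed here.

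Size:

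- Uncovered onset window: 24 − 2 = 22 hours after each infusion.
- Planned infusions, both arms together: 20 subjects × 4 = 80 at most.
- Effect of one misclassified subject on an arm's incidence: 1/10 = 10 percentage points with 10 per arm. The visible text gives 20 subjects and 1:1 allocation but not the arm sizes. If the split were 12 and 8, the effect would be 1/12 = 8.3 or 1/8 = 12.5 points.

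The first two figures describe exposure and the third describes sensitivity. None estimates how many reactions are missed.

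**The case against.** The strongest reply is that nothing is lost. A prolonged or delayed reaction that is rated possibly or probably related, or that is serious, is a primary safety event under another heading. Protocol 14.4.2 already asks for a display of events in the first 24 hours with no limit on duration. Section 3.1 of the SAP Addendum puts all TEAEs into summary tables. No test depends on the hypersensitivity line, the unblinded DSMB monitors safety, and the definition is consistent across documents. On this view only a labelling preference remains.

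Most of that stands, and it rules out several stronger readings that a reader might infer.

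- That the primary safety results omit these reactions. They do not: only a non-serious reaction judged unrelated leaves the primary list. There is also no composite count for anything to be missing from.
- That the most serious cases are the ones excluded. Duration is not seriousness, which Protocol 13.2.1.2 defines by outcome, nor is it severity, which Protocol 13.2.3 grades by limitation of activity and intervention. A serious prolonged reaction counts as an SAE.
- That hypersensitivity is the leading expected risk. Protocol 13.2.1.3 names transient donor-specific antibodies and vascular-access risks, and most of the risk discussion in Protocol 5.4 is blacked out.
- That premedication pushes onset beyond 2 hours. The documents do not say so.
- That the SAP dropped the 24-hour display. The readable text of SAP 7.1 and Addendum 3.1 does not repeat it, but SAP Section 8 does not list it as dropped and the final table list in Appendix F is blacked out.

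The objection does not supply the missing rate. The related-TEAE line and the full TEAE tables cover every kind of event, and the 24-hour summary is not restricted to hypersensitivity. The Addendum also says that adjudicated events will be listed but not summarized, which makes an explicit row more useful.

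**Conclusion.** The gap is real. Immediate reactions lasting 24 hours or more, and reactions starting after 2 but before 24 hours, are classified as neither hypersensitivity nor immune sensitization syndrome. As a measure of infusion reactions, the hypersensitivity line can only equal or fall below the true incidence in each arm. It remains a correct count of its own narrow definition.

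The consequence is misclassification in one descriptive rate. No formal test is affected, and the events are visible elsewhere. The size cannot be estimated, because the documents give neither a reaction rate nor a distribution of onset or duration. On the assumption of about 10 subjects per arm, each misclassified subject is worth about 10 percentage points in that arm. That is enough to justify a small addition to the tables, but not to change the endpoint.

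**What to change.** Keep the hypersensitivity endpoint as defined. Add one supplementary row to the safety summary: subjects with any hypersensitivity-type TEAE, whether adjudicated or investigator-reported, with onset within 24 hours of an infusion and regardless of duration. Show it by arm beside the defined endpoint. If it enters through the Addendum, label it post hoc.

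Two details should be stated with the row. The first is which event terms count as hypersensitivity-type; the list should be fixed without reference to treatment arm. The second is whether each event comes from adjudicated or raw data, since SAP 7.1 bases its summaries on adjudicated events and Addendum 3.1 on raw ones.

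The cost is one row, drawn from the events within 24 hours of dosing that Protocol 14.4.2 already requires to be summarized. No new data collection or change to clinical conduct is needed. The drawback is that the reported reaction rate may be higher.
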